10.6.3 Health economic evaluation

A within-trial economic evaluation in the form of a cost-utility analysis will be undertaken to measure the cost-effectiveness of the intervention compared with standard care. A National Health Service (NHS) and personal social services (PSS) perspective will be adopted for the analysis as recommended by the National Institute for Health and Clinical Excellence (NICE, 25). The incremental cost-effectiveness ratio (ICER) for the analysis will be the cost per Quality Adjusted Life Year (QALY) gained at 12 months. Utilities for the calculation of QALYs will be measured using the EQ-5D-5L administered at baseline, and six and 12 months post-randomisation. Participant level resource use will be combined with unit costs to estimate total costs for each participant in the trial. Unit costs will be obtained from publicly available sources, for example, the NHS reference costs (25) and the Personal Social Services Research Unit (PSSRU) Unit Costs of Health and Social Care (26).

Protocol Number, Version 1.0_FINAL_27.04.2016

Costs will include those associated with the implantation of the device (cost of device, cost of surgery, surgery review appointments) and those associated with participants' use of the health service over the study period. Costs associated with low vision training will not be included in the analysis as these are research costs and common to both arms. Health service use will be collected at six and 12 months post-randomisation using the Health Service Use Questionnaire. A secondary analysis will explore participants' out-of-pocket expenses associated with participants' own purchase of visual aids.

Multiple regression methods will be used to estimate incremental (differential) costs and QALYs with and without adjustment for participant baseline characteristics. Standard methods will be used to explore and display uncertainty in the cost-effectiveness data including a scatterplot on the costeffectiveness plane and a cost-effectiveness acceptability curve (CEAC). The curve will show the probability of the intervention being more cost-effective than standard care at different threshold levels of willingness-to-pay (WTP) per QALY gained. Sensitivity analysis will be performed to assess the robustness of the cost-effectiveness results to changes in key parameters. Since the time horizon of the analysis is one year, it will not be necessary to discount costs and effects. Details of the analysis will be incorporated in to the SAP.

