7 STUDY DESIGN

7.1 Study Design

The project will be a multicentre randomised controlled trial which will evaluate the efficacy, safety and cost-effectiveness of a novel intraocular telescopic lens (OriLens). We will enrol participants with bilateral advanced stable AMD who have had previous cataract surgery (bilateral pseudophakia). Surgical implantation of the OriLens will be carried out within eight weeks of randomisation. Primary and secondary outcomes will be assessed at one, three, six and 12 months post randomisation.

Those who fulfil the inclusion criteria will be randomised equally (stratified by site) to one of two groups: Group One (Surgical Intervention) will undergo implantation of the OriLens device as a secondary surgical procedure in addition to usual standard of care; Group Two (Conventional Intervention- Control) will receive usual standard of care.

In addition, a number of participant specific parameters will be evaluated to assess the impact of these factors on participant outcomes. Specifically, the study will evaluate the following using data collected during the study.

- 1. Does the type, size and location of the scar/atrophy or the preferred retinal locus (PRL) have an impact on visual outcome?
- 2. Does implantation in the aiming dominant/non-dominant eye produce a better outcome?
- 3. Do participants who have good binocular function pre-operatively, find use of the telescopic device more difficult?
- 4. Do pre-operative binocular vision abnormalities impact on acceptance and use of the device?
- 5. Does implantation of the device cause a change in visual summation and does this impact on the tolerability of the device?

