8.3.1 Intervention description

Group 1: Intervention

The implantation of the OriLens device will be carried out as a secondary surgical procedure no more than eight weeks post randomisation. Participating surgeons will be trained in the surgical procedure for implantation at the beginning of the trial: an instructional video developed by the research team will be available and the CI may observe the first procedure at each site at the request of the PI. The degree of difficulty of this intervention is considered to be small for experienced cataract surgeons. The pupil will be dilated. Local anaesthetic will be used according to the individual surgeon's preference. A minimal incision of 5.5 millimetres is recommended. The wound can either be a scleral flap or tunnel according to the surgeon's preference. The anterior chamber will be filled with viscoelastic and the implant will also be covered in viscoelastic material before insertion. It is important that the optic does not come into contact with the forceps. The orientation of the device should be checked: the lens should vault backwards and the end of the superior haptic should point to the right. Both loops of the device are to be placed in the sulcus. Implantation should not proceed if there is evidence of zonular or existing intraocular lens instability. All viscoelastic will be removed at the end of the surgery. Closure of the incision will be according to surgeon's preference. A peripheral iridotomy is not a routine requirement but may be carried out at the surgeon's discretion. An intracameral injection of antibiotics and a subconjunctival injection of steroids will be administered according to the surgeon's preference. Post-operative management is similar to phacoemulsification surgery and is according to the surgeon's preference. Participants will be prescribed combined steroid/antibiotic drops for use four weeks post-operatively. A standard surgical report documenting the details above will be completed post-operatively.

If the pupil is <2.5 mm in diameter, small sphincterotomies should be performed at the time of implantation of the device. Recording of concomitant medications during medical history is required to determine presence of such which may have an effect on pupil size.

Refraction, spectacle prescription and provision and three 45 minute sessions of low vision training as per the trial manual will follow post-operatively as per section 10.2.

Group 2: Control

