8.5 Participant Timeline

Eligibility will be determined at the screening visits. Surgery in Group 1 will take place at Day 0 with surgical review on days one and seven and study visits for both Groups at months one, three, six and 12. As the presence of the device is obvious to the casual observer, it will not be possible to mask assessors. Participants can also not be masked to the intervention. However, the final BCDVA measurement at 12 months will be duplicated by an additional observer independent to the trial and this measurement will be used for the primary analysis. BCDVA (primary outcome) will be measured with 4-meter ETDRS charts. Assessment at screening will include medical history, ophthalmic examination, confrontation visual field testing, visual acuity, reading speed, refraction, contrast sensitivity, assessment with x2.5 external telescope for distance and near vision, assessment for ocular dominance, binocular visual function, endothelial cell density, ocular coherence tomography (OCT) with volume scan, colour fundus photography, IVI, and EQ-5D-5L. Fundus fluorescein angiography (FFA) will be carried out in addition to OCT at baseline and only subsequently if clinically indicated as OCT cannot be performed post implantation of the device. The order of screening examinations will follow as per Figures 3 and 4, however, this may vary at site depending on the location of equipment. The detailed schedule is shown below in Table 2.

If all inclusion criteria are met at both screening visits, participants will be enrolled into the study. The required clinical information will be returned to the lead site (NICTU) and the study eye will be selected. The participant will be informed within 72 hours regarding which eye has been selected as the study eye and will be provided with a date to attend for Nd:YAG capsulotomy in the study eye, if not already done. After the participant has undergone the laser treatment, the Principal Investigator (PI) or designee will contact the CTU to determine group allocation. The participant will then be notified within 72 hours post laser treatment regarding group allocation.

Group 1 Care Pathway:

- Day 0: Surgery (surgical implantation of OriLens device)
- Day 1: Surgical review
- Day 7: Surgical review
- Assessments will be carried out at Months 1, 3, 6 and 12
- Low vision training at months 1, 3 and 12

Group 2 Care Pathway

- Day 0: No procedure

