10.2 Data Collection

10.2.1 Screening/Baseline Visit and Procedures

The screening tests will be conducted as per Section 8.7.2 above during two screening visits. The following baseline questionnaires will be administered at the end of the second screening visit:

- Health related quality of life (EQ-5D-5L)
- Vision-related quality of life (IVI)

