10.2.2 Study Visits and Procedures

Pre-randomisation (Day -20 to -7) (Both groups)

Nd: YAG Capsulotomy in study eye (if not already done)

Pre-operative (Day -7 to -1) (Intervention group only)

Pre-op medical history assessment Visual acuity (distance only) and ophthalmic examination Informed consent for surgical procedure

Day 0 (Intervention group only)

Surgical procedure Standard surgical report (post-operatively)

Day 1 Post-operative (Intervention group only)

Medical history, ophthalmic examination Visual acuity (Distance only) Adverse events check

Day 7 Post-operative (Intervention group only)

Medical history, ophthalmic examination

Visual acuity (distance and near), reading speed, refraction, and contrast sensitivity Adverse events check

1 Month (approximately 6-8 weeks post randomisation) (Both groups)

Medical history, ophthalmic examination Visual Acuity (distance and near), reading speed, refraction, and contrast sensitivity Spectacle prescription dispensing and voucher for glasses Visual Rehabilitation training Adverse events check

3 months (approximately 14 weeks post randomisation) (Both groups)

Medical history, ophthalmic examination Visual Acuity (distance and near), reading speed, refraction, and contrast sensitivity Visual Rehabilitation training Adverse events check

6 months (approximately 6-7 months post randomisation) (Both groups)

Medical history, ophthalmic examination Visual Acuity (distance and near), reading speed, refraction, and contrast sensitivity Health related quality of life (EQ-5D-5L) Vision-related quality of life (IVI) Health service use questionnaire Spectacle prescription dispensing and voucher for glasses Adverse events check

12 months (approximately 12-13 months post randomisation) (Both groups)

Medical history, ophthalmic examination Visual Acuity (distance and near), reading speed, refraction, and contrast sensitivity Fundus photography Specular microscopy Health related quality of life (EQ-5D-5L) Vision-related quality of life (IVI) Health service use questionnaire Spectacle prescription dispensing Visual Rehabilitation training Adverse events check

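### EQ-5D-5L is not measured between baseline and month 6, so the implant arm's wait, surgery and early recovery are unobserved and the incremental QALY may be biased in either direction

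*Protocol*

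**What the plan says.** - **Utility times.** Section 10.6.3: "Utilities for the calculation of QALYs will be measured using the EQ-5D-5L administered at baseline, and six and 12 months post-randomisation". Sections 10.2.2 and 10.3 and Table 2 agree. The baseline value comes from screening: "The following baseline questionnaires will be administered at the end of the second screening visit" (10.2.1), which Table 2 places before laser and randomisation.
- **What falls in the first interval in the implant arm.** Section 7.1: "Surgical implantation of the OriLens will be carried out within eight weeks of randomisation"; section 8.3.1 gives the same limit, "no more than eight weeks post randomisation". Section 8.5: "Surgery in Group 1 will take place at Day 0 with surgical review on days one and seven". Section 8.3.1: "Participants will be prescribed combined steroid/antibiotic drops for use four weeks post-operatively".
- **Adaptation.** Section 8.5 lists, for both groups, "Low vision training at months 1, 3 and 12". Section 10.4 says the implant arm needs this training in order to adapt fully to the device.
- **Visits already held.** Both arms attend at Months 1 and 3 for acuity, reading speed and contrast sensitivity (10.2.2, Table 2). EQ-5D-5L is not taken then.
- **Costs and analysis.** Section 10.6.3 counts the device, the surgery and the surgical reviews. It takes cost per QALY at 12 months as the result, plans sensitivity analysis on key parameters that it does not name, and leaves further detail to the SAP.

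**The concern.** The wait, the operation and the early recovery have no counterpart in the control arm, so randomisation does not cancel their effect on utility. With values only at baseline, month 6 and month 12, the path over the first six months has to be assumed. A post-operative dip would not be seen, and neither would an early gain. The same operation enters the cost side of the ratio completely. Cost-effectiveness is a stated secondary objective (6.3.2). The measurement schedule is fixed in the protocol, so this cannot be left to the SAP: a SAP can choose how to join the points, but it cannot supply utilities that were not collected.

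**Working it through.** The protocol states no utility, QALY or cost-effectiveness figure, so there is none to reproduce. The check asks how far a three-point straight-line rule can lie from plausible true paths.

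**Inputs from the protocol.** Utilities at weeks 0, 26 and 52, with the screening value placed at week 0. Wait *w* from randomisation to surgery: up to 8 weeks (7.1, 8.3.1), or about 1 to 3 weeks from Table 2, which puts randomisation at Day -20 to -7.

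**Assumptions.** Straight-line joining. Control utility flat. A utility gain *D* = 0.05 present at week 26 and held. A dip *d* lasting *r* weeks after surgery; *r* = 4 is borrowed from the period of drops, which is not itself evidence of utility loss. After the dip, either the full gain arrives at once ("step"), or utility returns to baseline and rises in a line to *D* at week 26 ("slow").

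**Formulas (QALYs over 52 weeks).**
- Three-point rule: (26 × D/2 + 26 × D)/52 = 0.75 D = 0.0375.
- True, step: [D(52 - w - r) - d r]/52.
- True, slow: [-d r + D(26 - w - r)/2 + 26 D]/52.

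| Wait (weeks) | Dip | Rise | True gain | Three-point rule against true |
|---|---|---|---|---|
| 1 | none | step | 0.05 × 51/52 = 0.0490 | 24% too low |
| 8 | none | step | 0.05 × 44/52 = 0.0423 | 11% too low |
| 3 | 0.05, 4 weeks | step | (2.25 - 0.20)/52 = 0.0394 | 5% too low |
| 8 | 0.05, 4 weeks | step | (2.00 - 0.20)/52 = 0.0346 | 8% too high |
| 8 | 0.05, 4 weeks | slow | (-0.20 + 0.35 + 1.30)/52 = 0.0279 | 34% too high |
| 8 | 0.10, 4 weeks | slow | (-0.40 + 0.35 + 1.30)/52 = 0.0240 | 56% too high |

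**Where the sign changes.** With no dip and the full gain arriving at week *x*, D(52 - x)/52 = 0.75 D gives x = 13. With a step after a dip, the rule overstates only if d > D(13 - w - r)/r. For D = 0.05 and r = 4 this is 0.0125 (8-week wait), 0.075 (3-week wait) or 0.10 (1-week wait).

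**Sensitivity to D.** For D from 0.03 to 0.10 the error runs from -24% to +98% of the true gain. The upper end is D = 0.03 with an 8-week wait, a 4-week dip of 0.10 and a slow rise: (-0.40 + 0.21 + 0.78)/52 = 0.0113 against 0.0225.

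**Size of a dip alone.** 0.05 × 4/52 = 0.0038 QALY; 0.10 × 4/52 = 0.0077 QALY.

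**What two more points would do.** Put Month 1 at week 7 and Month 3 at week 14 (10.2.2 gives about 6-8 and 14 weeks after randomisation).
- 1-week wait, no dip, step: 0.05 × (3.5 + 45)/52 = 0.0466 against a true 0.0490. The error shrinks from -0.0115 to -0.0024.
- 8-week wait, 4-week dip of 0.10, slow: utility at week 14 is 0.05 × 2/14 = 0.0071, so (0.025 + 0.343 + 1.30)/52 = 0.0321 against a true 0.0240. The error shrinks from +0.0135 to +0.0081.
- 8-week wait, 4-week dip of 0.05, step: 0.05 × (3.5 + 38)/52 = 0.0399 against a true 0.0346. The error grows from +0.0029 to +0.0053, because the dip falls between the two visits.

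**The case against.** A reader might infer that the plan overstates the QALY gain because only the implant arm can suffer a surgical dip. The documents do not support that. The protocol states no straight-line or area-under-the-curve rule, and the SAP, which may state one, is not at hand. Even under a straight line, benefit that arrives before month 6 is under-credited, and that too happens only in the implant arm. For an immediate 0.05 gain at week 8, the rule credits 0.5 × (8/52) × (8/26) × 0.05 = 0.0012 QALY before surgery but misses 0.5 × (18/52) × (18/26) × 0.05 = 0.0060 after it. The existence of any gain is also an assumption: none of the five EQ-5D-5L dimensions listed in 10.3 is vision.

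A reader might also infer that every possible loss of utility falls in the first interval. It does not. Removal or repositioning of the device and retinal detachment are listed as anticipated events, and adverse events are recorded to month 12. The later questionnaires can pick up lasting effects.

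Two further points carry weight. Section 8.3.1 likens post-operative management to that of routine cataract surgery, so a large or long dip has no support in the documents. And the Month 1 visit may miss the dip: at 6-8 weeks after randomisation it can fall at or before an operation done at week 8.

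What does not stand is that the matter can wait for the SAP. The planned sensitivity analysis could test an assumed decrement, but it cannot replace measured utilities. A slow gain is also not far-fetched, since post-operative spectacles are first prescribed at Month 1 and the second training session is at Month 3.

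**Conclusion.** The point holds as a gap in measurement. Utility is unobserved over the wait, surgery and early recovery in one arm, while the cost of that surgery is fully counted. Under an assumed straight-line rule and an assumed gain of 0.05, the plan would report 0.0375 QALY where the true gain could be about 0.024 to 0.049. The bias is upward with slow recovery or adaptation or a large dip, and downward if most of the benefit arrives before about week 13 after randomisation. The sign and size depend on the gain, the dip, the wait and the shape of recovery, none of which can be settled from the protocol. A claim that cost-effectiveness will look better than it is would go further than the documents allow. The primary outcome is unaffected. The change should be made, because the missing values cannot be recovered later.

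**What to change.** 1. Add EQ-5D-5L at the existing Month 1 and Month 3 visits in both arms, and amend Table 2 and sections 10.2.2, 10.3 and 10.6.3 to match.
2. State that QALYs are computed from actual assessment dates counted from randomisation. This also needs the visit clock to be reconciled. Section 8.5 sets Day 0 at surgery in Group 1, while 7.1 and 10.6.3 count from randomisation. After an 8-week wait, a month 6 visit counted from surgery falls nearly 8 months after randomisation, against 6 to 7 months in control (Table 2). The wait implied by Table 2 and the eight-week limit in 7.1 and 8.3.1 should be reconciled too.
3. Name a post-operative utility decrement, varied in size and length, as one of the sensitivity analyses planned in 10.6.3.

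The cost is two short extra questionnaires per participant at visits already held, read aloud to some. The added points do not reduce the error on every path: a dip confined to the first weeks after surgery would be only partly captured or missed, as the last worked case shows. That is why the third item is needed alongside the first.

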10.6.4 Additional analyses

Planned additional analyses will be described in the SAP.

10.6.5 Missing data

Every effort will be made to minimise missing baseline and outcome data in this trial. The level and pattern of the missing data in the baseline variables and outcomes will be established by forming appropriate tables and the likely causes of any missing data will be investigated. This information will be used to determine whether the level and type of missing data has the potential to introduce bias into the analysis results for the proposed statistical methods, or substantially reduce the precision of estimates related to treatment effects. If necessary, sensitivity analyses will be performed using multiple imputation or Bayesian Methods for missing data as appropriate.

10.6.6 End of Study

The end of trial will be when database lock occurs for the final study analysis. The study will be stopped early if;

- 1. Mandated by the research ethics committee
- 2. Mandated by Sponsor
- 3. Mandated by regulatory authorities
- 4. Recommended by the TSC
- 5. If funding ceases

11 METHODS: MONITORING

b.4 Assessment of safety

The safety of device will be assessed at each visit by noting any surgical complications during or after surgery, including visual acuity, position and clarity of the device and corneal clarity. From previous studies it is known that loss of corneal endothelial cells following implantation of devices such as this is often biphasic i.e., there is an initial decrease following surgery then a continued loss for some months but at a lower rate. Stabilisation usually occurs at 12 months (13-16). The corneal endothelial count will therefore be repeated at month 12. It is not anticipated that the device itself will cause any systemic adverse events. A record will be kept of all Serious Adverse Events (SAEs). The CI will be responsible for informing the Sponsor, the Research Ethics Committee and all study sites about any SAEs. The DMEC will provide information on all SAEs on a routine basis.

b.4.1 Analysis of safety data

Adverse events (AEs, SAEs) will be listed and summarised by treatment. Incidents will be listed and summarised by treatment. Responses to the recent falls question will be tabulated. Endothelial cell densities will be listed.

11.2 Interim analyses

In order to assess recruitment progress, an internal pilot study will be undertaken to assess feasibility which will run until month six of the recruitment period (month 12). By this time, it is anticipated that 20 participants will have been recruited and all sites will have been opened.

At the end of the pilot, the following analysis will be completed:

- Recruitment rate: % recruited versus target recruitment number
- % randomised based on total number screened

Recruitment feasibility milestones will be as follows: If recruitment rates achieve 75-100%, the trial will progress. If only 50-75% recruitment is achieved, the trial will progress following review of screening logs and the protocol and once barriers to achieve adequate recruitment are addressed. If 25-50% of the required number are recruited, the trial will progress only after screening logs and the protocol are reviewed and once, following approval by NIHR-EME, additional sites are opened. Should recruitment be <25%, it is not expected that the trial will progress; this decision will be made by the TSC.

An interim analysis will also be conducted to analyse efficacy and safety parameters. In relation to efficacy, an independent t-test will be applied with a *p* value <0.001 according to the Haybittle-Peto stopping rule. For safety, intraoperative complications are not anticipated to be significant. There is a potential risk of corneal endothelial cell damager in those who have been implanted with the device. Therefore, corneal clarity will be assessed at each clinic visit.

